9.6 Data management

Maternal interviews are conducted at enrollment and up to two additional time points, depending on the gestational age at enrollment. An outcome interview is conducted by telephone after the end of pregnancy, typically within 4-6 weeks after the estimated date of delivery (EDD). Medical records are requested from the delivery facility (maternal and neonatal information), obstetric provider (maternal information), pediatrician (neonatal/infant) and any specialty physician (maternal and neonatal/infant information). Data are abstracted from medical records using a standard abstraction form, and this information is entered into the study database by trained personnel. Hard copies of all study forms and hard copies and/or electronic copies of medical records are retained in the OTIS Research Center at the University of California San Diego.

9.6.1 Data handling conventions

Initial identification of major structural defects is performed by the study Data Coordinator, and then verified and classified by the Study Manager using the CDC coding manual (CDC, 2007). Final validation of the classification of all major birth defects reported in the study will be conducted by the OTIS Co-Investigator with expertise in the diagnosis of birth defects. All prenatal exposures to medications and vaccines are coded using the Slone Drug Dictionary (<http://sites.bu.edu/slone-drug-dictionary/>).

Twins or higher order multiples are handled as one pregnancy outcome. For example, if the pregnancy ends in at least one live born infant, the outcome is considered a live born outcome. If either or both twins have a major birth defect, the outcome is considered one major birth defect outcome. Twins are excluded from analyses of preterm delivery, small for gestational age infants, and postnatal growth.

Lost-to-follow-up status is designated if a participant withdraws from the study before the outcome of pregnancy is known or reported, or if study staff are unable to make contact with

the study participant within 12 months of the estimated end of pregnancy in order to obtain outcome information. Participants who are lost-to-follow-up but who have at least one day of follow-up after enrollment are included in time-to-event outcomes such as spontaneous abortion if they are otherwise eligible for inclusion in that analysis.

Table 6 Denominators by outcome

Outcome	Denominator
Major Structural Birth Defects Among Live Births	Pregnancies ending in live birth with exposure in the first trimester for benralizumab cohort, and other comparison groups at least one malformed infant in an individual pregnancy is considered one malformed outcome
Major Structural Birth Defects Among All Pregnancies	Pregnancies with any outcome excluding those lost-to-follow-up; with exposure in the first trimester for benralizumab cohort, and other comparison groups; at least one malformed fetus/infant in an individual pregnancy is considered one malformed outcome
Spontaneous Abortion	Pregnancies enrolled in the study prior to 20.0 weeks' gestation with at least 1 follow-up data collection point after enrollment date. Exposure can occur any time in pregnancy prior to the event.
Preterm Delivery	Pregnancies enrolled prior to 37.0 weeks' gestation and ending in at least one live born infant. Excludes twins or higher order multiples due to inherent higher risk of preterm birth in multiples. Exposure can occur any time in pregnancy prior to the event.
Small for Gestational Age Infants	Pregnancies ending in at least one live born infant; excluding twins or higher order multiples due to the inherent higher risk of reduced birth size in multiples. Exposure can occur any time in pregnancy prior to the event.
Still birth	All pregnancies, excluding lost-to-follow-up. Exposure can occur any time in pregnancy prior to the event.
Elective Termination	All pregnancies, excluding lost-to-follow-up. Exposure can occur anytime in pregnancy prior to the event.
Postnatal Growth	Pregnancies ending in at least one live born infant with pediatric growth records available at approximately 1 year of age. Multiples are excluded. Exposure can occur anytime in pregnancy.

Coding of outcomes is performed by the study staff using the definitions provided in the protocol. Interview, diary, and examination data will be recorded on hardcopies of forms, medical records and medical record abstraction forms may be recorded on hardcopies or electronically; these records will be retained in the Coordinating Center. Data from all forms will be extracted and entered into a customized database located in the Coordinating Center. The data will be extracted and entered by trained study personnel with extensive experience with this type of information. Entries will be periodically reviewed for logical errors, and intake and outcome forms will be validated for data entry accuracy.

The primary source for information collected on demographics and exposures is by maternal interview, as the participant typically provides more accurate information than the medical records, especially in regards to non-prescription medications and any medications not taken as prescribed. Doses, dates, and timing of exposure are confirmed with medical records. If the medication is administered in the office, the medical record is the primary source; if the medication is administered at home and there is a discrepancy between the record and maternal report, the participant is contacted and asked about the discrepancy.

The medical record is the primary source for type of prenatal test, date, and results of prenatal tests, disease diagnosis, and infant outcomes, including birth and postnatal growth, and major structural defects.

Data included in the interim reports is cumulative, therefore data may change when additional information is received either by maternal report or by medical records.

The method and duration of storage of data is addressed in the informed consent. Access to the database will be controlled by password. Hardcopies of participant files, original oral consent signed and dated by the interviewer, signed consent forms, and original signed medical record release forms will be kept in a locked file room, in locked cabinets, and scanned into an electronic file, under the supervision of the OTIS Research Center.

Missing values for the critical data for OTIS studies are typically very few and nearly always less than 10%. There is generally no need to include imputation strategies; however, depending on the prevalence of missingness, sensitivity analyses will be conducted. These will be specified in the SAP.

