9.3.2 Outcome definitions

- **Major Structural Birth Defects:** a major structural defect is defined and classified using the CDC coding manual (CDC, 2007), as reported by the mother and validated through the medical record. The CDC coding manual is utilized to classify defects reported through the ongoing population-based Metropolitan Atlanta Congenital Defects Program (MACDP) and is based on agreed-upon criteria by CDC investigators for major structural defects regardless of etiology. Infant medical records are abstracted by the data coordinator, and reviewed by the study manager. Final validation of the classification of

all major birth defects reported in the study will be conducted by the OTIS Co-Investigator with expertise in the diagnosis of birth defects.

- **Preterm Delivery:** preterm delivery is defined as a spontaneous or induced delivery at <37 gestational weeks, reported by the mother and validated through the medical record. Please refer to Section 9.3.1 for further description of the method for defining gestational age and therefore preterm birth.
- **Small for Gestational Age (SGA) Infants:** Live born infants who are \leq 10th centile on birth weight, length and/or head circumference for infant sex and gestational age will be considered small for gestational age. The U.S. Centers for Disease Control and Prevention (NCHS) growth charts will be used for full term infants, and preterm growth charts will be used for preterm infants (Lubchenco, 1966). The outcomes of birth weight, length and head circumference are reported by the mother and validated through the medical record.
- **Spontaneous Abortion:** Spontaneous abortion is defined as spontaneous pregnancy loss prior to 20.0 weeks' gestation. In this study, since women enroll after recognition of pregnancy, spontaneous abortions are only identified after enrollment in clinically recognized pregnancies. This outcome is reported by the mother and validated through the medical record.
- **Stillbirth:** Stillbirth is defined as a fetal death that occurs \geq 20 weeks' gestation. This outcome is reported by the mother and validated through the medical record.
- **Elective Termination:** Elective termination is defined as deliberate interruption of pregnancy by surgical or medical means.

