9.4 Data sources

Maternal Interviews: In all three study groups, data are collected by semi-structured maternal telephone interview on two to four occasions during, and shortly after completion of pregnancy. The interviews include data on exposure timing, dose, and duration for all medications, including benralizumab, taken anytime in pregnancy as well as data on a wide variety of confounders (See Section 9.3.3).

For women exposed to benralizumab or other asthma medications, information on disease severity/symptom control from the Asthma Control Test is obtained directly from the mother at each maternal telephone interview. In addition, information on asthma related hospitalizations and physician visits is collected at the enrollment interview and each of the subsequent maternal interviews. At the conclusion of pregnancy, regardless of the outcome, participants are interviewed about the outcome including presence or absence of birth defects, pregnancy and infant complications and infant size. At this time point the Asthma Control Test questions are asked again to reflect the last four weeks of pregnancy. In addition, asthma treatment regimen at first day of last menstrual period for the current pregnancy according to GINA guidelines will be used to classify disease severity.

Medical Records: Mothers are asked to release medical records to the study investigators from their obstetrician or other obstetric provider, specialty care provider such as allergist/pulmonologist, hospital of delivery, pediatrician, and other health care provider specialists involved in the pregnancy. These records are abstracted and used to validate pregnancy outcomes, collect information on health and growth of the child, and when necessary to provide details regarding timing or dose of benralizumab and other asthma medications in the absence of clear information from maternal report. Self-reported prescriptions used for GINA

classification will be validated with medical record information where available. Pre-defined definitions for each of the study outcomes are used for classification.

Validation of final classification of major birth defects, the primary outcome, that have already been identified by the study Data Coordinator and verified and classified by the Study Manger, is conducted periodically and before each annual and final study report by the study Co-Investigator, a specialist in dysmorphology/teratology.

Table 4 Variables collected per cohort

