9.7.2 Exploratory/sensitivity analyses

Exploratory analyses addressing potential effect modifiers such as Asthma Control Test measures of disease symptom control, and measures of asthma exacerbation will be addressed.

In addition, sub-analyses based on length and gestational timing as well as dose of exposure to benralizumab will be performed.

Stratified analyses based on prenatal diagnostic test performed prior to enrollment in the study will be conducted for the primary endpoint. The purpose of this analysis is to address the inherent bias in excluding women at the time of enrollment in the cohort study who have already received prenatal diagnosis of a major structural birth defects, but including women who have already had a normal result or prenatal diagnosis for major structural birth defects prior to enrollment. Therefore, the planned stratified analysis will compare the birth prevalence of major structural birth defects among the subset of women enrolled in the cohorts prior to prenatal diagnostic testing to detect structural defects (ultrasound for structure, chorionic villus sampling, amniocentesis), to the birth prevalence of major birth defects among the subset of women enrolled in the cohorts after prenatal diagnostic testing to detect structural defects.

Regarding asthma severity, the measures are only captured after enrollment, and in the exposed group only after being on treatment, so they would typically not be included in the analysis as adjustment factors as they could be mediators. However, descriptive analyses of the balance in cohorts on measures of disease severity are presented. Sub-analyses or

sensitivity analyses within disease severity categories can be performed, depending on the distribution of the covariates. This would be described in detail in the SAP.

Sub-analyses excluding chromosomal or known genetic anomalies (classified by study investigators as having a known genetic etiology) will also be conducted. Details will be provided in the SAP.

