9.7.4 Assessment of cases for a signal of major structural birth defects

An aggregate assessment of cases with major structural birth defects will be conducted at each interim report and for the final report for the study. This assessment will be conducted by the investigators and reviewed by the Scientific Advisory Board members. The assessment will consist of the following steps:

- 1 a review of specific birth defects for any evidence of a cluster of similar multiple malformations, or clusters of similar isolated major birth defects among exposed pregnancies that does not occur in the comparison pregnancies;
- 2 a review of alternative aetiologies for the specific birth defects clusters, such as family history or co-exposures;
- 3 a review of the biologic plausibility of the gestational timing of exposure to the medication relative to the embryologic timing of initiation of the specific birth defect(s);
- 4 a review of the cumulative published literature for any evidence consistent with the occurrence of that cluster of defects with exposure to the medication in pregnancy.

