9.8 Quality control

As noted in Section 9.6, quality control measures are in place throughout the entire period of data collection and data entry. Training and retraining of study staff is monitored per study Standard Operating Procedures, and validation of data entry for critical study variables is conducted for 100% of study maternal interviews. Data exported for interim reports and final

analyses for this study are checked for logical errors, and range checks are performed. All major structural birth defect classifications are verified by the study investigators. Data are reviewed on an interim basis by the VAMPSS external advisory committee (See Section 12.1.2). Final data sets are cleaned and utilized for preparation of the analyses and study reports. All analyses (coding and output) are reviewed by the OTIS Research Center lead study statistician and at least one other staff statistician. Study reports are reviewed by the Study Manager and the Investigators. All data sets and analytic files are archived indefinitely at the OTIS Research Center, and analyses can be replicated as necessary.

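### Classification of the primary outcome is described without masking to cohort, and one reclassified case moves the expected primary ratio by about 11 to 19%

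*Protocol*

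**What the plan says.** Four sections of the protocol describe how a major structural defect, the primary outcome, is classified.

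- **9.3.2** takes its definition from the CDC coding manual, which it describes as "based on agreed-upon criteria by CDC investigators for major structural defects regardless of etiology". Infant records are abstracted by the data coordinator and reviewed by the study manager.
- **9.6.1** gives the sequence: "Initial identification of major structural defects is performed by the study Data Coordinator, and then verified and classified by the Study Manager", using the same manual. Then: "Final validation of the classification of all major birth defects reported in the study will be conducted by the OTIS Co-Investigator".
- **9.4** repeats the last step and adds its timing. The text beginning "Validation of final classification of major birth defects, the primary outcome, that have already been identified by the study Data Coordinator" places it periodically and before each annual and final report, in the hands of a Co-Investigator who specialises in dysmorphology and teratology.
- **9.8** adds: "All major structural birth defect classifications are verified by the study investigators".

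None of the four mentions masking to cohort, a classifier outside the study team, or independent duplicate review.

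Three other places bear on who knows the cohort.

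- **9.7.4** has a cluster review at every interim report that sets exposed against comparison pregnancies: "This assessment will be conducted by the investigators and reviewed by the Scientific Advisory Board members".
- **Section 11** has major defects in benralizumab-exposed pregnancies sent to the sponsor within 24 hours of awareness. Comparator defects are not on that route.
- **Table 4** lists exposure validation and defects under the same medical record abstraction.

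A separate call on genetic cause appears in 9.7.2: "Sub-analyses excluding chromosomal or known genetic anomalies (classified by study investigators as having a known genetic etiology) will also be conducted".

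**The concern.** Whether a finding counts as a major defect is sometimes a borderline call, and knowing the exposure can tilt such a call either way. An assessor may count a doubtful exposed case out of caution, or dismiss it as unrelated. If this happens differently by cohort, the ratio is biased, and neither a larger sample nor a wider interval corrects it.

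The protocol gives classifiers a realistic chance of knowing cohort. An exposed case can go out as a serious adverse event before the periodic final validation takes place. The investigators who verify classifications are also the group that compares exposed with comparison cases, and 9.7.4 does not exclude the validating Co-Investigator. The same classifications serve twice: they form the primary estimate, and they feed the pattern review that Section 9.9 relies on to interpret a possible chance association.

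The protocol itself fixes the steps, roles, manual and timing of classification, so masking belongs in this text and is not merely a detail for the SAP. With few events expected, a single changed call is visible in the estimate.

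**Working it through.** **Inputs.** From Section 9.5 and Table 5: 180 exposed and 270 treated-asthma pregnancies with complete outcome, and 3% prevalence in the unexposed. From 9.7.1 and 9.7.3: a covariate counts as a confounder if it changes the exposure estimate by 10% or more. From 9.7.1: relative risks are reported with 95% and 80% intervals and, by 9.5, without formal testing.

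**Step 1. Reproduce the plan's figures.** Take two independent binomials, Bin(180, 0.03 × RR) and Bin(270, 0.03), and sum exactly the probability that the observed ratio is strictly above 1.5. Zero comparator events with at least one exposed event counts as exceeding.

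| True RR | Table 5, X = 1.5 | Recomputed |
|---|---|---|
| 1 | 0.19 | 0.187 |
| 2 | 0.70 | 0.698 |

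The X = 2.0 and 3.0 columns of the defect block also agree. The X = 1.2 column agrees when exact ties are counted (0.377 against 0.38 at true RR 1). Table 5 is sound on its own inputs.

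**Step 2. Expected events at no effect.** Exposed: 180 × 0.03 = 5.4. Comparator: 270 × 0.03 = 8.1. Ratio: (5.4/180)/(8.1/270) = 1.00.

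**Step 3. Change one case.**

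| Change | Formula | Ratio | Shift |
|---|---|---|---|
| Exposed +1 | (6.4/180)/(8.1/270) | 1.19 | +18.5% |
| Exposed −1 | (4.4/180)/(8.1/270) | 0.81 | −18.5% |
| Comparator +1 | (5.4/180)/(9.1/270) | 0.89 | −11% |
| Comparator −1 | (5.4/180)/(7.1/270) | 1.14 | +14% |

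In whole numbers, 5 v 8 events gives (5/180)/(8/270) = 0.94, 6 v 8 gives 1.12, and 4 v 8 gives 0.75. Every one-case shift in the table exceeds 10%.

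**Step 4. Effect on the Table 5 probabilities,** with the same strictly-above-1.5 rule. If one extra exposed case is always accepted, the probability at true RR 1 rises from 0.19 to 0.27. If one exposed case is always rejected (counts floored at zero), the probability at true RR 2 falls from 0.70 to 0.61. Section 9.5 summarises these two probabilities as below 20% and at least 70%.

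**Step 5. Compare with sampling error.** By the log method at 5.4 v 8.1 events, SE = √(1/5.4 − 1/180 + 1/8.1 − 1/270) = √0.2994 = 0.547.

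- 95% interval: exp(±1.96 × 0.547) = 0.34 to 2.92.
- 80% interval: exp(±1.2816 × 0.547) = 0.50 to 2.02.

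A one-case shift lies well inside both.

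**The case against.** The strongest reply is that the plan is silent rather than wrong. No section says the classifiers know the cohort, and an operating procedure not shown here may already mask them. Classification also follows an external code list, uses the medical record as its primary source for defects, and passes through three roles ending with a specialist. Any ratio built on so few events will move when one case changes; that is arithmetic, not evidence of bias, and the protocol gives no rate of borderline calls.

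Most of this stands, and it limits the point to an improvement. It does not remove it. The manual and the three steps narrow discretion but mask nobody, the steps are sequential, and the last rests with one Co-Investigator. The interval reflects chance only, so differential misclassification lies outside it. If a masking procedure exists, citing it settles the matter.

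A reader might infer more than the text supports:

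- **That the genetic-etiology call shifts the primary ratio.** It does not. The primary endpoint counts defects whatever their cause (9.3.2, 9.7.1), and cases "classified by study investigators as having a known genetic etiology" drop out only in sub-analyses.
- **That the classifiers also enrol and interview the women, or re-judge settled cases each year.** No section says so. Section 9.4 times the validation, and 9.6.1 allows data to change when new information arrives.
- **That the point estimate alone carries the conclusion.** It is reported with two intervals and read beside the cluster review.
- **That one call could move the ratio from 0.94 to 1.29.** That requires 5 v 8 to become 6 v 7, which is two changes in opposite directions.

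**Conclusion.** The point holds as a cheap improvement to how the primary outcome is ascertained, not as an error in the analysis. The protocol specifies the classification chain in four sections without masking to cohort, while other sections show that cohort is known among the investigators and that only exposed defects are flagged to the sponsor.

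One changed case moves the primary ratio by about 11 to 19%. That is more than the 10% the protocol treats as material for a confounder, and much less than the sampling error. The 10% figure is borrowed as a yardstick; the protocol does not apply it to classification.

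The size rests on the Table 5 planning figures and a true ratio of 1. The probability shifts in Step 4 further assume that exactly one exposed case is always called the same way. How often a borderline call would arise, and in which direction it would go, is unknown. The documents do not show that classification is in fact biased or unmasked.

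**What to change.** State in Sections 9.3.2 and 9.6.1, with 9.4 and 9.8 brought into line, that:

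1. The Co-Investigator's final major/minor classification, and the genetic-etiology call used for the 9.7.2 sub-analyses, are made from an infant or fetal abstract with cohort, asthma and maternal medication fields removed where feasible.
2. Cases from all three cohorts are classified in the same batch.
3. The classification is recorded before cohort is revealed for the 9.7.4 review.
4. A case with new records is reclassified under the same masking.
5. Reporting of serious adverse events within 24 hours proceeds unchanged, handled by staff other than the masked classifier.

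If an operating procedure already does this, a reference to it is enough.

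The cost is a short protocol addition, a redacted export of the existing abstraction form and some preparation time. No extra assessor is needed. Masking will be imperfect where an infant record mentions the mother's treatment, or where the classifier has already seen the case at an earlier cluster review.
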